7.5 SECONDARY ENDPOINT(S)

7.5.1 Key secondary endpoint(s)

[figure not shown]
This section is not applicable as no key secondary assessment has been specified in the study.

[figure not shown]
7.5.2 (Other) secondary endpoint(s)

[figure not shown]
This section is not applicable as no secondary assessment has been specified in the study.

7.7 EXTENT OF EXPOSURE

Not applicable.

7.8 SAFETY ANALYSIS

If any AEs/SAEs are reported for screening failures, these will be summarised in the AE listing "Adverse event overall summary" and described in the Clinical Study Report (CSR) if considered related to the screening procedures.

7.8.1 Adverse events (procedure related)

Only procedure related AEs are recorded and analyses will be performed on the OBS subjects.

These events will be coded using the most recent version of MedDRA.

The analyses of adverse events will be descriptive in nature. All analyses of AEs will be based on the number of subjects with AEs and not the number of AEs.

For analysis, multiple AE occurrence data on the electronic case report form (eCRF) will be collapsed into one event provided that all of the following applies:

- All AE attributes are identical
- The occurrences were time-overlapping or time-adjacent (time-adjacency of 2 occurrences is given if the second occurrence started on the same day or on the day after the end of the first occurrence)

For further details on summarization of AE data, please refer to Analysis and Presentation of AE data from clinical trials '[14] and "Handling of missing and incomplete AE dates" [7].

Other significant AEs will be reported and summarized according to ICH E3 [16] criterion. Thus, AEs classified as 'other significant' will include those non-serious adverse events with:

- (i) 'action taken = discontinued from study', or
- (ii) marked hematological and other lab abnormalities, or lead to significant concomitant therapy as identified by the Clinical Monitor / Investigator at an MQRM or a RPM.

An overall summary of adverse events will be presented by subject group.

The frequency of subjects with adverse events will be summarized by subject group, primary SOC and PT. Separate tables will be provided for subjects with serious adverse events and with other significant adverse events.

The SOCs will be sorted according to the standard sort order specified by the European Medicines Agency (EMA), PTs within SOC will be sorted by descending relative frequency.

For disclosure of AE data on ClinicalTrials.gov, the frequency of subjects with non-serious AEs (procedure related) occurring with an incidence of greater than 5 % (in preferred terms) will be summarised by primary SOC and PT. The frequency of subjects with SAEs will also be summarised.

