5.9.6.1 Definitions of AEs

Adverse event

An adverse event (AE) is defined as any untoward medical occurrence, including an exacerbation of a pre-existing condition, in a patient or clinical investigation subject undergoing a study procedure (e.g. MRI with a contrast agent) according to the study protocol.

An AE can therefore be any unfavorable and unintended sign (including an abnormal laboratory finding), symptom, or disease temporally associated with a study procedure, whether or not considered related to the study procedure.

Serious adverse event

A serious adverse event (SAE) is defined as any AE which:

- results in death
- is life-threatening

- requires inpatient hospitalization or prolongation of existing hospitalization
- results in persistent or significant disability or incapacity
- is a congenital anomaly/birth defect
or
- is to be deemed serious for any other reason if it is an important medical event when based upon appropriate medical judgment which may jeopardize the subject and may require medical or surgical intervention to prevent one of the other outcomes listed in the above definitions

Life-threatening in this context refers to an event in which the subject was at risk of death at the time of the event; it does not refer to an event that hypothetically might have caused death if more severe.

For Japan only: the following events will be handled as “deemed serious for any other reason”:

AEs which possibly lead to disability will be reported as SAEs.

Intensity of AEs

The intensity of the AE should be judged based on the following:

Mild:	Awareness of sign(s) or symptom(s) that is/are easily tolerated
Moderate:	Enough discomfort to cause interference with usual activity
Severe:	Incapacitating or causing inability to work or to perform usual activities

Causal relationship of AEs

Medical judgment should be used to determine the relationship, considering all relevant factors, including pattern of reaction, temporal relationship, confounding factors such as concomitant medication, concomitant diseases and relevant history.

Yes: There is a reasonable causal relationship between a study procedure and the AE.
No: There is no reasonable causal relationship between a study procedure and the AE.

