5.9.6.2 Adverse event collection and reporting

AE Collection and Reporting

The following must be collected and documented on the appropriate eCRF by the Investigator:

- From signing the informed consent onwards until individual subject's Visit 7/ discontinuation visit:
All AEs (serious and non-serious), which are associated with any study procedure.

The Investigator should enter SAEs, and non-serious AEs which are relevant for the SAE immediately (within 24 hours) into the eCRF. The same timeline applies if SAE follow-up information becomes available.

Information required

For each AE, the Investigator should provide the information requested on the appropriate eCRF pages.

The Investigator should determine the causal relationship to the study procedures outlined under [Section 6.2](#).

All (S)AEs, including those persisting after individual subject's study completion of study must be followed up until they have resolved, have been sufficiently characterized, or no further information can be obtained.

Reporting of related Adverse Events associated with any BI drug

The investigator is encouraged to report all adverse events related to any BI drug according to the local regulatory requirements for spontaneous AE reporting at the investigator's discretion by using the locally established routes and AE report forms. The term AE includes drug exposure during pregnancy, and, regardless of whether an AE occurred or not, any abuse, off-label use, misuse, medication error, occupational exposure, lack of effect, and unexpected benefit.

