6.2 DETAILS OF STUDY PROCEDURES AT SELECTED VISITS

6.2.1 Screening period

An informed consent will be obtained prior to subject's participation in the study. Considering the number and complexity of study procedures and the duration of the study, the subjects should be given sufficient time to discuss concerns, potential benefits and risks, and obligations. Restrictions according to [Section 4.2.2](#) are allowed only after the subject signs the informed consent. If the subject is willing to provide a sample for unspecified pharmacogenomic testing, a separate consent must be obtained. If the subject is willing to participate in the MRI subset (only at selected study sites) a separate consent must be

obtained. Each subject will be assigned a unique subject number and once the subject signed informed consent, enrollment will be recorded in eCRF.

At Visit 1, demographics, medical history (including baseline conditions), physical examination, BMI, vital signs (including pulse oximetry) and eligibility criteria will be assessed. Concomitant therapy, smoking status, MESI and AE (if study procedure related) will be recorded. Subjects will be provided with a reminder diary (see [Section 3.1.1](#)).

Visit 1 should be scheduled to start in the morning between 6:00 am and 9:00 am. Restriction check, pregnancy test (if applicable) and IRT subject visit registration should be done first. The sequence of procedures will be mMRC, followed by ECG and pre PFT. Post PFTs should be done prior to post DLCO. 6 MWT should be performed after post PFTs/DLCO. Blood samples for safety laboratory and PGx testing should be collected after the ECG procedure is completed.

Instructions for shipping of laboratory samples will be provided in the manual. If the subject has met all the eligibility criteria, Visit 2 will be scheduled.

Discontinuation during the screening period

If subjects discontinue from the study during the screening period, no additional clinic visits are required, and they will be marked as screen failures.

Subjects who were discontinued during screening period under the criteria of the former protocol version can re-enter the study if they meet the amended inclusion/exclusion criteria. In this case, the subject will receive a new subject number and be treated like a new subject (e.g. new informed consent).

Re-screening

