7.3.4 Safety analyses

All subjects enrolled will be included in the safety analysis. In general, safety analyses are descriptive in nature and are based on BI standards. No hypothesis testing is planned. Adverse events (AEs) will be coded using the latest version (at the time of database lock) of Medical Dictionary for Regulatory Activities (MedDRA) coding dictionary. Standard BI summary tables and listings will be produced by subject groups.

Statistical analysis and reporting of AEs will focus on AEs that are study procedure related as judged by the investigators and medical events of special interest (MESI) as defined in [Section 5.7.](#)

Frequency, severity, and causal relationship of AEs will be tabulated by system organ class and preferred term after coding according to the latest version of MedDRA. Frequency of MESIs will be tabulated by disorder.

Laboratory data will be analyzed both quantitatively as well as qualitatively. The latter are done via comparison of laboratory data to their reference ranges. Values outside the reference range as well as values defined as clinically relevant will be highlighted in the listings.

Subject groups will be compared descriptively with regard to distribution parameters as well as with regard to frequency and percentage of patients with abnormal values or clinically relevant abnormal values.

Vital signs, physical examinations, or other safety-relevant data observed at screening, baseline, during the course of the study and at the end-of-study evaluation will be assessed with regard to possible changes compared to findings before start of treatment.

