7.11 ANALYSIS OF COVID-19 IMPACT

There is currently an outbreak of respiratory disease, COVID-19 worldwide which has impacted the conduct of this trial. This public health emergency has raised more difficulties for patients to meet protocol-specified procedures, e.g. adhering to protocol-mandated visits and laboratory/diagnostic testing. Site personnel or trial patients are also under the risk to get infection with COVID-19.

Consequently, there are unavoidable protocol deviations due to COVID-19 illness and/or COVID-19 public and individual health control measures. To assess the impact the following analyses are planned:

[figure not shown]
- Subjects with potentially protocol deviations (PDs) related to COVID-19 in the study will be documented in the Covid log file [c38560938].
- Frequency of the patient with missed relevant visits or early discontinued from study due to COVID-19 and related PDs will be listed and analysed descriptively.
- SARS-CoV-2 infection as well as AEs related to SARS-CoV-2 infection will be listed (if applicable).

[figure not shown]
8. **REFERENCES**

[figure not shown]
8.1 **PUBLISHED REFERENCES**

[figure not shown]
[1]	CPMP/ICH/363/96: "Statistical Principles for Clinical Trials", ICH Guideline Topic E9; Note For Guidance on Statistical Principles for Clinical Trials, current version.
[4]	BI-VQD-12045_40-413 : "Identify and Manage Important Protocol Deviations (iPD) ", current version, DMS for controlled documents.
[5]	Examining the Genetic Factors That May Cause Chronic Obstructive Pulmonary Disease (COPD) (COPDGene)
	ClinicalTrials.gov Identifier: NCT00608764
[6]	MacIntyre N et al. Standardisation of the single-breath determination of carbon monoxide in the lung. European Respiratory Journal. 2005; 26: 720-735 [R06-2002].
[7]	BI-KMED-BDS-HTG-0035 : "Handling of missing and incomplete AE dates", current version; DMS for controlled documents.

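### SAP 7.8.1 treats every recorded adverse event as procedure related, although the protocol collects events regardless of causality and plans to tabulate the causality judgement

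*SAP*

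**What the plan says.** Protocol 5.9.6.1 includes in its definition of an AE any sign, "symptom, or disease temporally associated with a study procedure, whether or not considered related to the study procedure". It then provides a two-level causality scale whose negative level reads "No: There is no reasonable causal relationship between a study procedure and the AE". Protocol 5.9.6.2 says what must be entered on the eCRF, from consent to Visit 7 or discontinuation: "All AEs (serious and non-serious), which are associated with any study procedure". It asks the investigator to determine causality for these events.

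Protocol 7.3.4 says that reporting will focus on AEs the investigator judges related to a procedure, and on medical events of special interest (MESIs). It also plans that "Frequency, severity, and causal relationship of AEs will be tabulated by system organ class and preferred term".

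Protocol 6.2.1, in the paragraph on Visit 1, uses a narrower rule: "MESI and AE (if study procedure related) will be recorded".

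SAP 7.8.1 carries the procedure-related label in its title and opens with "Only procedure related AEs are recorded and analyses will be performed on the OBS subjects". Its outputs are an overall summary, tables by system organ class and preferred term, tables of serious and other significant AEs, and the ClinicalTrials.gov tables. In that disclosure the non-serious AEs are labelled procedure related. SAP 7.8.2 (laboratory) and 7.8.4 (ECG) repeat the condition that a finding becomes an AE if procedure related. SAP 4.2 states that the planned analyses have not changed from the protocol.

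SAP 7.11 plans, where applicable, a listing of SARS-CoV-2 infections and of AEs related to them. It does not say which data that listing is drawn from.

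**The concern.** Association with a procedure and causal relation to it are different things, and the protocol separates them within one sentence of 5.9.6.1. The SAP merges them. A table headed procedure related tells its reader that the investigator attributed those events to a study procedure. If the table holds every AE collected under 5.9.6.2, that statement is wrong for each event judged unrelated, and the error would pass into the public registry.

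The causality judgement is also the only information that separates the two kinds of event. The protocol promises to tabulate it and SAP 7.8.1 does not mention it. In a study with no investigational product, whose AE reporting concerns the safety of procedures such as CT, contrast MRI and sputum induction, that split carries most of the meaning of the AE tables.

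**Working it through.** No arithmetic applies: the documents state no AE count, rate or causality proportion. The check sets the texts side by side and follows each reading through to the output.

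**Step 1: what decides whether an event is recorded.**

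| Place | Condition for being an AE, or for being recorded |
|---|---|
| Protocol 5.9.6.1 | In time with a procedure, related or not |
| Protocol 5.9.6.2 | Associated with any procedure; causality judged afterwards |
| Protocol 5.9.1, 5.9.3, 5.9.4 (examination, laboratory, ECG) | Associated with a procedure |
| Protocol 6.2.1 (Visit 1) | Related to a procedure |
| Protocol 6.2.2 (observational period) | AE review, no relatedness condition |
| SAP 7.8.1, 7.8.2, 7.8.4 | Related to a procedure |

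Where the protocol says associated for laboratory and ECG findings, the SAP says related.

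**Step 2: is related only a synonym for associated?** Three texts speak against it. Protocol 5.9.6.1 contrasts the two words. Protocol 7.3.4 focuses reporting on AEs judged related, which presupposes a wider recorded set. SAP 7.8 describes screening-failure AEs in the study report only if they are considered related to screening procedures, so the SAP itself allows for recorded AEs that are not.

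**Step 3: follow each reading.**

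- *Sites followed 5.9.6.* The database holds causality Yes and No. SAP 7.8.1 gives no rule for selecting on causality, because its premise is that there is nothing to select. All events then go into tables labelled procedure related. The bracket in the registry sentence could be taken as a filter, but the SAP does not say so.
- *Sites recorded only related events.* The label is correct, but collection departs from 5.9.6.2 and the tabulation in protocol 7.3.4 has a single category, Yes.
- *Sites differed.* AE frequencies from about 50 sites mix two definitions.

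Following both documents as written gives the first case.

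**Step 4: is the difference declared?** No. SAP 4.2 reports no change, and SAP 4.3 does not mention AE recording.

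**Step 5: the COVID-19 listing.** An AE attributed to infection would not ordinarily be procedure related, so under the premise of 7.8.1 few would be in the AE data. Infections can be entered as MESIs, which need no link to a procedure (protocol 5.7). Pneumonia is a named MESI. COVID-19 is not, and the category Other is at the investigator's discretion. The COVID log file in SAP 7.11 is for protocol deviations. Possible sources therefore exist, but none is named and complete capture is not assured.

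**The case against.** The strongest reply is that this is loose wording. The rule for sites is protocol 5.9.6.2, and a sentence in an analysis plan does not change what sites enter. Protocol 7.3.4 already announces a focus on procedure-related AEs, and the SAP heading may simply follow it. SAP 7.8.1 also refers to an internal standard on presenting AE data, which is not among the documents and may contain a causality table. The safety analysis is descriptive, there is no investigational product, and AEs are not a main outcome.

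Much of this stands, and it rules out several stronger readings that a reader might infer.

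- *That events judged unrelated have been lost.* The narrow rule in protocol 6.2.1 belongs to Visit 1, protocol 6.2.2 has none, and 5.9.6.2 requires collection throughout. Loss at Visit 1 is a risk only.
- *That the causality tabulation has no valid source.* Under 5.9.6.2 it has one.
- *That the COVID-19 listing would be empty and read as no impact.* MESIs can carry these events, and SAP 7.11 separately analyses missed visits and discontinuations due to COVID-19.
- *That AE counts are inflated by some factor.* The documents give no proportion judged unrelated, and SAP 7.8.1 counts subjects with AEs, not events, so a ratio of event counts would not carry over to its tables.

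The reply does not remove the labelling problem. If sites did follow 5.9.6.2, as it argues, the label in the SAP and in the registry table is wrong for events judged unrelated.

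**Conclusion.** The inconsistency is real and bears on how safety results are reported. SAP 7.8.1, echoed in 7.8.2 and 7.8.4, rests on a statement about recording that protocol 5.9.6 contradicts. It leaves out the causality tabulation planned in protocol 7.3.4, and SAP 4.2 does not acknowledge either difference. If the collection rule was followed, events judged unrelated would be published as procedure related.

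The scope is all AE tables and the registry disclosure, in a study of up to 455 subjects. The number of subjects affected cannot be derived from the documents. The main outcomes (lung density, lung function, exacerbations) are untouched. The conclusion assumes that the causality judgement required by the protocol is held in the database, and that the internal AE standard does not already impose the missing split; neither can be checked here. The point is worth correcting before the final tables are produced, but it does not show that safety data are missing.

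**What to change.** In SAP 7.8.1:

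1. Delete the clause stating that only procedure-related AEs are recorded.
2. Tabulate all recorded AEs as associated with a study procedure.
3. Show the subset with causality = Yes separately, by system organ class and preferred term. This delivers the tabulation planned in protocol 7.3.4.
4. Use the procedure-related label only for that subset, including in the ClinicalTrials.gov disclosure.

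Align the wording of SAP 7.8.2 and 7.8.4 with protocol 5.9.3 and 5.9.4. With these edits the no-change statement in SAP 4.2 would hold on this point.

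Reconcile the Visit 1 wording in protocol 6.2.1 with 5.9.6. SAP version 4.0 already concerns the end-of-study analyses, so if collection is complete, state in the study report which recording rule sites applied.

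In SAP 7.11, name MESI records and the discontinuation reasons recorded under protocol 3.3.5.1, as well as AEs, as sources for the SARS-CoV-2 listing.

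The cost is a few sentences of SAP text, one added split using a judgement the protocol already requires, and possibly one sentence in the study report. No new data are needed.

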7.8.2 Laboratory data

The analyses of laboratory data are descriptive in nature and are based on BI standards [15], where the process of standardisation and normalisation as well as standard analyses for safety laboratory data is described. The OBS will be used for this analysis. Clinically relevant abnormal values or changes in laboratory test results will be recorded as adverse event (if procedure related) or baseline condition in the eCRF.

7.8.3 Vital signs

Descriptive statistics by subject group over time including change from baseline will be performed for vital signs (blood pressure and pulse rate). The OBS will be used for this analysis. Clinically relevant changes in vital signs that are recorded as an AE in the eCRF will be analysed as planned in Section 7.8.1.

7.8.4 ECG

[figure not shown]
A standard 12-lead ECG is performed at screening, 52 weeks, 104 weeks and 156 weeks. The OBS will be used for this analysis. Any clinically relevant findings from this examination are recorded under baseline conditions or adverse events (if procedure related) in the eCRF. No separate tables/listings are planned for the report.

7.8.5 Others

A physical examination (body weight, body height, BMI) is performed at screening, 52 weeks, 104 weeks and 156 weeks. The OBS will be used for this analysis. Descriptive statistics for weight and/or BMI by subject group over time including change from baseline will be presented.

7.9 MEDICAL EVENTS OF SPECIAL INTEREST (MESIS)

Specific disorders related to the underlying COPD disease as defined in the CSP, Section 5.7, will be collected during the study. MESI are analysed per AE standards based on PPSBM subjects. The frequencies of these MESIs will be summarised by disorder and intensity following the same order as in the eCRF. A separate listing by subject group and disorder will be created including additional information of start/end date, outcome, provided therapy, and intensity of the event.

7.10 OTHER ASSESSMENTS

Pulse oximetry, BODE index and 6 minute walk test will be analysed descriptively.

7.11 ANALYSIS OF COVID-19 IMPACT

There is currently an outbreak of respiratory disease, COVID-19 worldwide which has impacted the conduct of this trial. This public health emergency has raised more difficulties for patients to meet protocol-specified procedures, e.g. adhering to protocol-mandated visits and laboratory/diagnostic testing. Site personnel or trial patients are also under the risk to get infection with COVID-19.

Consequently, there are unavoidable protocol deviations due to COVID-19 illness and/or COVID-19 public and individual health control measures. To assess the impact the following analyses are planned:

[figure not shown]
- Subjects with potentially protocol deviations (PDs) related to COVID-19 in the study will be documented in the Covid log file [c38560938].
- Frequency of the patient with missed relevant visits or early discontinued from study due to COVID-19 and related PDs will be listed and analysed descriptively.
- SARS-CoV-2 infection as well as AEs related to SARS-CoV-2 infection will be listed (if applicable).

[figure not shown]
8. **REFERENCES**

[figure not shown]
8.1 **PUBLISHED REFERENCES**

[figure not shown]
[1]	CPMP/ICH/363/96: "Statistical Principles for Clinical Trials", ICH Guideline Topic E9; Note For Guidance on Statistical Principles for Clinical Trials, current version.
[4]	BI-VQD-12045_40-413 : "Identify and Manage Important Protocol Deviations (iPD) ", current version, DMS for controlled documents.
[5]	Examining the Genetic Factors That May Cause Chronic Obstructive Pulmonary Disease (COPD) (COPDGene)
	ClinicalTrials.gov Identifier: NCT00608764
[6]	MacIntyre N et al. Standardisation of the single-breath determination of carbon monoxide in the lung. European Respiratory Journal. 2005; 26: 720-735 [R06-2002].
[7]	BI-KMED-BDS-HTG-0035 : "Handling of missing and incomplete AE dates", current version; DMS for controlled documents.
